2. SCHEDULE OF ACTIVITIES (SOA)

Table 1 Schedule of Activities

Procedure	Pre-Screening ^a (Visit 0)	Screening ^a (Visit 1)	Study Visits									Early Withdrawal	Follow Up (up to 28 days post last dose)
			2	3	4	5	6	7	8	9	10		
Study Day			-7	1	14	28	56	84	112	140	168		
Assessment Window	-30 d		±0d	+ 3d	±3d	±3d	±3d	±3d	±3d	±3d	±3d		
Eligibility													
Informed consent	X												
Genetic Sample Informed Consent ^b	X												
Demography	X												
COPD Exacerbation History	X												
Pre-Screening Fibrinogen ^c	X												
Smoking History ^d		X											
Smoking Status ^d		X	X										
Inclusion and Exclusion criteria		X											
Medical history ^e		X											
Full physical examination including height and weight		X											
Chest x-ray (CXR) ^f		X											

Procedure	Pre-Screening ^a (Visit 0)	Screening ^a (Visit 1)	Study Visits									Early Withdrawal	Follow Up (up to 28 days post last dose)
			2	3	4	5	6	7	8	9	10		
Study Day			-7	1	14	28	56	84	112	140	168		
Assessment Window	-30 d		±0d	+3d	±3d	±3d	±3d	±3d	±3d	±3d	±3d		
HIV, Hepatitis B and C screening ^g		X											
Pulse Oximetry		X											
Additional Eligibility and In Study Assessments													
Verify Eligibility ^h			X	X									
Brief Physical				X				X			X	X	X
Urine or serum pregnancy test ⁱ		X		X		X	X	X	X	X	X	X	
Laboratory assessments (clinical chemistry (includes liver chemistries), hematology, urinalysis)		X		X		X					X	X	X
Additional Liver chemistries only					X		X	X					
12-lead ECG		X		X		X		X			X	X	
Vital signs	X	X		X		X		X			X	X	
Spirometry		X		X				X			X	X	
Randomization				X									
Dispense Study Medication				X		X	X	X	X	X			

Procedure	Pre-Screening ^a (Visit 0)	Screening ^a (Visit 1)	Study Visits									Early Withdrawal	Follow Up (up to 28 days post last dose)
			2	3	4	5	6	7	8	9	10		
Study Day			-7	1	14	28	56	84	112	140	168		
Assessment Window	-30 d		±0d	+3d	±3d	±3d	±3d	±3d	±3d	±3d	±3d		
Dispense log pad and provide training			X										
Dispense MDI sensors and provide training			X										
Dispense physical activity monitor and provide training			X										
Study treatment				←=====→									
Study treatment compliance (ediary)				←=====→									
Collect IP					←=====→							X	X
Collect MDI sensors					←=====→							X	X
Collect physical activity monitor					←=====→							X	X
Collect log pad					←=====→							X	X
Adverse Event (AE) review				←=====→								X	X
Serious Adverse Event (SAE) review	←=====→				←=====→							X	X

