4. OBJECTIVES AND ENDPOINTS

Objectives	Endpoints

Primary
 
 • To characterize the dose response of danirixin compared with placebo on the incidence and severity of respiratory symptoms in participants with COPD • To compare the safety of danirixin with placebo in participants with COPD 	
 • Change from baseline in respiratory symptoms measured by E-RS:COPD daily diary at month 6: total score and subscales (i.e. breathlessness, cough and sputum, and chest symptoms) • Adverse events (AE), clinical laboratory values, vital signs, electrocardiogram (ECG)

Objectives	Endpoints

Secondary
 
 • To characterize the dose response of danirixin compared with placebo on the annual rate of moderate/severe COPD exacerbations in participants with COPD • To further characterize the clinical activity of danirixin compared to placebo in participants with COPD 	
 • Healthcare Resource Utilization (HCRU)-defined COPD exacerbations • E-RS:COPD Responder Analysis (including subscales) • Number of Exacerbations of Chronic Pulmonary Disease (EXACT) tool defined events • Time to first EXACT event • EXACT event severity • EXACT event duration for all events • Time to first HCRU-defined COPD exacerbation • Time to first severe HCRU-defined COPD exacerbation • HCRU-defined exacerbation duration • Change from baseline for the St. George's Respiratory Questionnaire (SGRQ) total score (derived from SGRQ-C) • SGRQ responder analysis • Change for baseline COPD Assessment Test (CAT) total score • CAT responder analysis • Lung function (FEV1, FEV1 % predicted, FVC, FEV1/FVC ratio) • Rescue medication use • Participant experience of physical activity (subset of approximately 50% of participants) measured using PROactive Clinic Visit Tool (C-PPAC)

Objectives	Endpoints

 To characterize the pharmacokinetics of danirixin in participants with COPD 	
 Danirixin concentration and standard pharmacokinetic parameters for danirixin (e.g. AUC, Cmax, Tmax), using dried blood spot data

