10.5.2. Safety Analyses

All safety endpoints will be tabulated or plotted by treatment group and will be performed on the mITT Population. Further details will be described in the RAP.

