12.2. Appendix 2: Clinical Laboratory Tests

- The tests detailed in [Table 5](#) Protocol-Required Safety Laboratory Assessments will be performed by the central laboratory, except as noted.
- Local laboratory results are only required in the event that the central laboratory results are not available in time for either study treatment administration and/or response evaluation. If a local sample is required, it is important that the sample for central analysis is obtained at the same time. Additionally, if the local laboratory results are used to make either a study treatment decision or response evaluation, the results must be entered into the CRF.
- Protocol-specific requirements for inclusion or exclusion of participants are detailed in [Section 6](#).
- Additional tests may be performed at any time during the study as determined necessary by the investigator or required by local regulations.

Table 5 Protocol-Required Safety Laboratory Assessments

Laboratory Assessments	Parameters			
Hematology	Platelet Count RBC Count Hemoglobin Hematocrit	RBC Indices: MCV MCH MCHC	WBC count with Differential: Neutrophils Lymphocytes Monocytes Eosinophils Basophils	
Clinical Chemistry ¹	BUN	Potassium Chloride Bicarbonate	Aspartate Aminotransferase (AST)/ Serum Glutamic-Oxaloacetic Transaminase (SGOT)	Total and direct bilirubin
	Creatinine	Sodium	Alanine Aminotransferase (ALT)/ Serum Glutamic-Pyruvic Transaminase (SGPT)	Total Protein
	Glucose (fasting required for screening)	Calcium	Alkaline phosphatase	
Routine Urinalysis	
 • Specific gravity 			

Laboratory Assessments	Parameters
	
 • pH, glucose, protein, blood, ketones by dipstick • Microscopic examination (if blood or protein is abnormal)
Other Screening Tests	
 • Plasma fibrinogen (a screening plasma fibrinogen is only needed for participants with 1 COPD exacerbation in the prior year) • Follicle-stimulating hormone and estradiol (as needed in women of non-childbearing potential only) • Serum or urine human chorionic gonadotropin (hCG) pregnancy test (as needed for women of childbearing potential)² • HIV antibody, hepatitis B surface antigen (HBsAg), and hepatitis C virus antibody³ • All study-required laboratory assessments will be performed by a central laboratory, with the exception of urine testing

NOTES:

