7.2.5 Rescue Medication	
 
Additional plots daily rescue medication use
 

7.3.1 E-RS: COPD Total Score	
 
Identify subgroups not required for final SAC
 

7.3.3 Time to First Clinically Important Deterioration	
 

 

8.3 Clinical Laboratory Analysis	
 
Remove urinalysis outputs because no PCI ranges are defined for urinalysis
 

8.4.5.1 Frequentist MMRM Methodology Specification	
 
Additional summaries of FEV1/FVC ratio and plots of arithmetic mean and 90% CIs for all spirometry endpoints.
 

11 Biomarker Analysis	
 
Additional tables and boxplots in subjects with pneumonia
 

14.4.1.1 Study Phases for Diary Data	
 
Clarify that Diary data phases applies to EXACT events
 

14.6.2 Study Population	
 
Additional COPD medication combinations table at Month 6
 

14.6.3 Efficacy	
 
Clarify definitions for Season, time to first, raw annual rate and offset. Remove definition of CID as not reporting this exploratory endpoint.
 

14.6.4 Safety	
 
Clarify definition for character laboratory parameters. Add definition of ICS use for pneumonia table.
 

14.11 Appendix 11: List of Data Displays	
 
Updates to tables and figures.
 
Remove urinalysis outputs
 
Remove CID tables
 

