### **8.3. Clinical Laboratory Analyses**

Laboratory evaluations including the analyses of Chemistry laboratory tests, Hematology laboratory tests and liver function tests will be based on GSK Core Data Standards.

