## 11. BIOMARKER ANALYSES

C-reactive protein and fibrinogen data will be summarized in the same way as laboratory data. Summary tables and boxplots for each treatment by visit (including screening, baseline, Day 84 and Day 168) will be generated for the mITT populations and also for the subset of subjects who have an event in the 'Infective pneumonia' SMQ.

Exploratory biomarker analysis will be the subject of a separate RAP.

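### The amended SAP plans no by-arm summary of urinalysis results, although urinalysis is a required safety laboratory test, and its reason (no PCI ranges) rules out only PCI-based displays

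*SAP*

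**What the plan says.** The primary safety objective in protocol section 4 is "To compare the safety of danirixin with placebo in participants with COPD". Its endpoints are listed as "Adverse events (AE), clinical laboratory values, vital signs, electrocardiogram (ECG"), with no laboratory panel carved out.

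Protocol Appendix 2, Table 5 (required safety laboratory assessments) includes "Routine Urinalysis". It covers specific gravity and dipstick pH, glucose, protein, blood and ketones, with microscopy only if blood or protein is abnormal. The Schedule of Activities has one row for "Laboratory assessments (clinical chemistry (includes liver chemistries), hematology, urinalysis"), marked at Visits 1, 3, 5 and 10, Early Withdrawal and Follow Up.

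On analysis, protocol 10.5.2 states: "All safety endpoints will be tabulated or plotted by treatment group and will be performed on the mITT Population". It leaves further details to the reporting and analysis plan.

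The SAP amendment log (1.1), under section 8.3, reads: "Remove urinalysis outputs because no PCI ranges are defined for urinalysis". The removal is logged again under Appendix 11. The operative text agrees with the log: SAP 8.3 says that evaluations including "Chemistry laboratory tests, Hematology laboratory tests and liver function tests will be based on GSK Core Data Standards", and does not mention urinalysis. SAP Table 1, which sets out changes from the protocol's planned analysis, has no row for it.

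**The concern.** A test required of every participant, and belonging to a primary endpoint, has no planned summary by treatment group, while the protocol says that all safety endpoints will have one. The justification is also narrower than the decision. A missing PCI range prevents a count of values outside that range. It does not prevent a shift table or a change-from-baseline summary.

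What is at stake is modest but real. A dose-related drift in dipstick protein, blood or glucose could consist of individually unremarkable results, none of which an investigator would report. Only a by-arm summary of the values would show such a pattern, and none is planned.

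**Working it through.** The plan states no figure to reproduce. The check traces urinalysis from endpoint to display, then tests the stated reason.

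**1. Does urinalysis belong to the endpoint?** The endpoint row says clinical laboratory values without naming panels. Protocol 9.4.4 points to Appendix 2 for the list of clinical laboratory tests, and Table 5 there lists urinalysis. So it does, by the protocol's own cross-reference.

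**2. What laboratory displays does the final analysis contain?** From SAP Appendix 11:

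| Display type | Numbers | Content | Urinalysis |
|---|---|---|---|
| Tables (14.11.7) | 3.16 to 3.21 (6) | 2 chemistry, 2 haematology, 2 hepatobiliary | 0 |
| Figures (14.11.8) | 3.2 to 3.5 (4) | ALT; ALT against bilirubin; 2 neutrophil | 0 |
| Laboratory listings (14.11.14) | 27 to 31 (5) | Chemistry and haematology PCI values; character results | None named |

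Listing 31 covers laboratory data with character results and might carry dipstick readings. It is a participant-level listing, not a summary by arm.

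**3. Does the lack of PCI ranges explain the omission?** SAP 14.8.1 has no urinalysis analyte, so the premise is true. It rules out the equivalents of Tables 3.17 and 3.19, the worst-case tables by PCI criteria. It does not rule out other forms that the SAP uses elsewhere:

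- Tables 3.16 and 3.18 summarise change from baseline for chemistry and haematology and need no PCI range.
- SAP 11 says "C-reactive protein and fibrinogen data will be summarized in the same way as laboratory data" (Tables 6.1 and 6.2), and neither analyte has an entry in 14.8.1.
- ECG findings are reduced to a worst post-baseline category (normal, abnormal, unable to evaluate) under SAP 14.6.4. A dipstick shift is a display of the same kind.

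A baseline rule for laboratory data (SAP 5.2) and an on-treatment rule (SAP 14.4.1.4) already exist.

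**4. What still reaches a by-arm display?**

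- Protocol Appendix 4 names urinalysis among the laboratory abnormalities that count as adverse events when the investigator judges them clinically significant. Those events enter the by-arm adverse event tables.
- Creatinine, BUN and glucose remain in the chemistry tables (3.16 and 3.17), with PCI limits in 14.8.1.
- Dipstick results not reported as adverse events reach no by-arm table or figure.

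**5. How much data is unsummarised?** Inputs from protocol 5.2: about 600 randomised and about 540 completing. The scheduled on-treatment visits with urinalysis are Visit 5 (Day 28) and Visit 10 (Day 168).

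- If all dropout comes after Day 28: 600 + 540 = 1,140 samples.
- If all dropout comes before Day 28: 540 + 540 = 1,080 samples.
- Per arm, with six equal arms: 600 / 6 = 100 randomised and 540 / 6 = 90 completing.

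Early Withdrawal and Follow Up samples are extra and are not counted. This measures the data left out of by-arm summaries. It is not an effect size.

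**The case against.** A fair opponent has several points.

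- **What was removed is unknown.** A reader might infer that a full set of by-arm urinalysis tables was planned and then deleted. SAP version 001 is not among the documents. The log says only that outputs were removed, and its reason would fit PCI-based tables or listings. The interim safety tables in the current SAP run from 3.1 to 3.23 without a gap and include no urinalysis. The point therefore rests on what the current SAP plans.
- **Urinalysis is not wholly uncompared.** A reader might infer that the safety comparison is silent on this domain. The adverse event tables and serum chemistry show otherwise. This stands, and it limits the gap to results not reported as adverse events.
- **No urinary signal is described.** The risk table in protocol 3.3.1 names testicular effects, host defence and embryofetal development. Protocol 10.5.4.3 lists hepatotoxicity, neutrophils, pneumonia and other infections as key safety endpoints. This lowers the importance of the gap, but the commitment in 10.5.2 does not depend on a prior signal.
- **The change is disclosed.** The log states it twice, with a reason, so concealment is not supported. A reader might also infer a data-driven choice, because the amendment describes the unblinded strategic interim in the past tense. Nothing in the documents shows that. Only the Table 1 row is missing.
- **10.5.2 defers details to the SAP.** That covers the form of a display. It does not comfortably cover having none for a required test.
- **SAP 8.3 is an inclusive list that relies on the sponsor's core standards, which are not available here.** That weakens 8.3 as evidence. The itemised display list in Appendix 11 does not have this weakness.
- **CRP and fibrinogen are imperfect comparators.** They are continuous biomarkers, whereas dipstick results are largely graded. The comparison holds for pH and specific gravity. For graded results, the ECG findings are the closer precedent.
- **Availability of the data is uncertain.** A line under the screening tests in Appendix 2 exempts urine testing from the central laboratory. It may mean only the pregnancy test, but it needs to be settled.

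**Conclusion.** The point holds in a limited form. The current SAP provides no by-arm summary of urinalysis values, against a protocol commitment covering all safety endpoints. The reason given supports dropping PCI-based displays only. The affected material is about 1,080 to 1,140 scheduled on-treatment samples, assuming about 600 randomised, about 540 completing and sampling as scheduled.

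The practical consequence is narrow: a shift in dipstick results not individually reported as adverse events would appear in no by-arm display. No efficacy conclusion is affected, and the documents give no reason to expect such a shift. The change is still worth making, because it restores part of a primary safety comparison at low cost.

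The conclusion rests on reading clinical laboratory values to include the tests in Appendix 2, Table 5, and on Appendix 11 being the full list of planned displays.

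**What to change.** 1. Confirm that urinalysis results are in the study database, and clarify the Appendix 2 line on urine testing outside the central laboratory.
2. Name urinalysis in SAP 8.3. Add to 14.11.7 one mITT table by treatment group showing the shift from baseline to the worst on-treatment dipstick category for protein, blood, glucose and ketones. Use the categories as recorded, since the documents define no grading scale.
3. Summarise pH and specific gravity as change from baseline, in the format of Tables 3.16 and 3.18.
4. If the outputs stay out, add a row to SAP Table 1 recording a change from protocol 10.5.2, with a rationale other than the absence of PCI ranges.

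If the data are in the database, the cost is SAP wording and one or two standard tables, with no new procedures. If results were kept only at sites, the cost would be higher and step 4 becomes the realistic option.

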## 2. SUMMARY OF KEY PROTOCOL INFORMATION

### 2.1. Changes to the Protocol Defined Statistical Analysis Plan

Changes from the originally planned statistical analysis specified in the protocol are outlined in [Table 1](#).

**Table 1 Changes to Protocol Defined Analysis Plan**

Protocol	Reporting & Analysis Plan	
Statistical Analysis Plan	Statistical Analysis Plan	Rationale for Changes

 
All Participants population
 
	
 
All Subjects population
 
	
 
R&D Clinical Data Standards Board (CDSB) recommendation to use the term 'Subjects' in all displays (Tables, Figures & Listings)
 

 
No Intent-to-treat (ITT) population
 
	
 
ITT population defined to be used for selected efficacy displays
 
	
 
Used for key efficacy displays to enable phase III planning
 

 
No Per Protocol (PP) population
 
	
 
PP population defined and used for efficacy displays
 
	
 
Remove data from participants who had a protocol deviation considered to impact efficacy during the treatment period.
 

 
No Symptomatic population
 
	
 
Symptomatic population defined and used for selected study population and efficacy displays
 
	
 
Used to explore the subgroup of symptomatic participants.
 

 
No PK2 population
 
	
 
PK2 population defined and used for PK dry blood spot vs wet whole blood
 
	
 
Used to compare dry blood spot with wet whole blood
 

 
mITT population used for efficacy endpoints
 
	
 
PP population used for efficacy endpoints
 
	
 
Remove data from participants who had a protocol deviation considered to impact efficacy during the treatment period.
 

 
The final Emax model will be repeated using months 1-6 and months 3-6.
 
	
 
The final Emax model will be repeated using months 2-6.
 
	
 
Team decision to include most informative time period.
 


 
The protocol states that exacerbation rates for the danirixin and placebo groups, along with the ratio in exacerbation rates danirixin/placebo, will be estimated and corresponding 95% credible intervals will be produced.
 
	
 
90% credible intervals will be produced for all Bayesian efficacy analyses including exacerbation rates.
 
	
 
Inconsistency in protocol.
 

## 2.2. Study Objectives and Endpoints

Objectives	Endpoints	Assessed in Strategic Interim
Primary Objectives	Primary Endpoints	

 
To characterize the dose response of danirixin compared with placebo on the incidence and severity of respiratory symptoms in participants with chronic obstructive pulmonary disease (COPD)
 
	
 
Change from baseline in respiratory symptoms measured by the Evaluating Respiratory Symptoms in COPD (E-RS: COPD) daily diary: total score and subscales (i.e. breathlessness, cough and sputum, and chest symptoms)
 
	Yes

 
To compare the safety of danirixin with placebo in participants with COPD
 
	
 
Adverse events (AE), clinical laboratory values, vital signs, electrocardiogram (ECG)
 
	Yes 
Secondary Objectives	Secondary Endpoints	

 
To characterize the dose response of danirixin compared with placebo on the annual rate of moderate/severe COPD exacerbations in participants with COPD
 
	
 
Healthcare Resource Utilization (HCRU)-defined COPD exacerbations
 
	Yes

 
To further characterize the clinical activity of danirixin compared to placebo in participants with COPD
 
	
 
E-RS: COPD Responder Analysis (including subscales)
 
	Yes
	
 
Number of Exacerbations of Chronic Pulmonary Disease (EXACT) tool defined events
 
	No
	
 
Time to first EXACT event
 
	No
	
 
EXACT event severity
 
	No
	
 
EXACT event duration for all events
 
	No
	
 
Time to first HCRU-defined COPD exacerbation
 
	Yes
	
 
Time to first severe HCRU-defined COPD exacerbation
 
	Yes
	
 
HCRU-defined COPD exacerbation duration
 
	Yes

 
Change from baseline for the St. George's Respiratory Questionnaire (SGRQ) total score (derived from
 
		Yes

Objectives	Endpoints	Assessed in Strategic Interim
	SGRQ-C)	
	
 
• SGRQ responder analysis
 
	Yes
	
 
• Change from baseline for the COPD Assessment Test (CAT) total score
 
	Yes
	
 
• CAT responder analysis
 
	Yes
	
 
• Lung function (forced expiratory volume in 1 second [FEV1], FEV1 % predicted, forced vital capacity [FVC], FEV1/FVC ratio)
 
	Yes
	
 
• Rescue medication use
 
	Yes
	
 
• Participant experience of physical activity (subset of approximately 50% of participants) measured using Clinical Visit PROactive Physical Activity in COPD Tool (C-PPAC)
 
	Yes 

 
• To characterize the pharmacokinetics of danirixin in participants with COPD
 
	
 
• Danirixin concentration and standard pharmacokinetic (PK) parameters for danirixin (e.g. AUC, Cmax, Tmax), using dried blood spot data
 
	No
Exploratory Objectives	Exploratory Endpoints	

 
• To further explore study participants' experience with study treatment and overall experience with the study
 
	
 
• Time to first Clinically Important Deterioration (CID)
 
	No
	
 
• SGRQ domains
 
	Yes

 
• To characterize the effect of danirixin on lung matrix destruction/remodelling
 
	
 
• Blood/serum/plasma biomarkers that are indicative of extracellular matrix turnover/remodelling (e.g. elastin and collagen neo-epitopes)
 
	No

 
• Comparison between dried blood spot and wet whole blood analysis of danirixin concentrations in participants with COPD
 
	
 
• Danirixin concentration and standard pharmacokinetic parameters for danirixin (e.g. AUC, Cmax, Tmax)
 
	No

Objectives	Endpoints	Assessed in Strategic Interim

 
To characterise danirixin exposure-response relationships for various safety parameters, if appropriate
 
	
 
Danirixin systemic exposure and various efficacy/pharmacodynamic (PD)/safety parameters, if appropriate
 
	No

[1] AEs, serious AEs (SAEs), drug-related AEs, AEs leading to withdrawal, AEs of special interest (AESI), laboratory data, ECG

[2] Summary of C-PPAC questionnaire responses only

